**INSTRUCTIONS**

This template is intended to help investigators prepare a protocol that includes all of the necessary information needed by the IRB to determine whether a study meets approval criteria. Read the following instructions before proceeding:

1. Use this protocol template for a PI initiated study that includes direct interactions with research subjects. Additional templates for other types of research protocols are available in the system Library.
2. If a section or question does not apply to your research study, type “Not Applicable” underneath.
3. Once completed, upload your protocol in the “Basic Information” screen in IRES IRB system.

## SECTION I: RESEARCH PLAN

1. Statement of Purpose: State the scientific aim(s) of the study, or the hypotheses to be tested.  
Investigating if giving post-operative dexamethasone to patients with a history of opioid use disorder on medication assisted treatment during pregnancy improves their pain scores and decreases their opioid use after cesarean section.
2. Probable Duration of Project: State the expected duration of the project, including all follow-up and data analysis activities.  
5-5.5 years of data collection followed by six months of data analysis and patient follow up
3. Background: Describe the background information that led to the plan for this project. Provide references to support the expectation of obtaining useful scientific data.

In August 2018, the CDC published data from 1999 – 2014 showing that the US national prevalence rate of deliveries of women with opioid use disorder had increased from 1.5 to 6.5 per 1,000 deliveries. Another recent study reported that 20-40% of pregnant women filled a prescription for opioids during their pregnancy, which does not account for opioids obtained illegally. Thus, rates are even higher if illegally obtained prescription opioid or heroin is considered. These are only a couple examples of data that have brought more attention to the effect of the national opioid crisis on the obstetrics in how opioid use among pregnant patients has risen dramatically.

Complications are still incurred even if women are able to manage their opioid use during pregnancy as relapse risk and developing OUD is much greater during the postpartum period than antenatally, which carries with it risks of repeated cycles of withdrawal, contraction of infectious diseases, and even overdose and death. For example, there were 211 maternal deaths in Colorado from 2004–2013 and 63 of them were by self-harm (accidental overdose or suicide). Most of these deaths occurred during the postpartum period and involved OUD (majorly opioid-related). Additionally, another recent study discusses how overdose is the leading cause of maternal associated deaths in Utah from 2004-2013, (69 of 113) with opioids being the leading cause of drug overdose. All of these deaths occurred in the postpartum period, which is thought to be due to increased stresses during delivery that carry into the postpartum period. Postpartum pain is one of these stresses, which is the area this study hopes to intervene on.

One major intervention that is now the gold standard for use in pregnant women with opioid use disorder is medication assisted treatment (MAT), as its use is associated with improvement in fetal and obstetric outcomes, including compliance with prenatal care, lower rates of preterm birth, reduced fetal and neonatal morbidity and mortality, and a higher likelihood of newborn being discharged to his/her parents.

Medication assisted treatment includes regular (at least once a day) use of methadone, buprenorphine or suboxone. As a review: methadone is a synthetic opioid agonist that eliminates withdrawal symptoms and relieves drug cravings by acting on our brain's opioid receptors. It occupies and activates these opioid receptors more slowly than other opioids such as heroin, morphine, and opioid pain medication. In an opioid-dependent person, treatment doses do not produce euphoria. It is unique amongst MAT options in that it must be given daily by a methadone clinic. Buprenorphine is a partial opioid agonist, meaning that it binds to opioid receptors but activates them less strongly than full agonists. It also reduces cravings and withdrawal symptoms in

a person with an opioid use disorder without producing euphoria. This medication can be prescribed by a physician who is specially certified. Suboxone is a partial opioid agonist plus an opioid antagonist (naloxone), which was developed to further prevent medication misuse. It can also be prescribed by physicians who are specially certified.

It is well established that patients with opioid use disorder have difficulty with pain control, as chronic opioid exposure induces tolerance to the analgesic effects of opioids. Thus for our pregnant patients who undergo cesarean delivery, traditional postpartum pain strategies that include systemic or neuraxial opioids are less effective, and these women require a significantly larger amount of opioids post-partum. Specifically, studies have showed that MAT maintained women have similar analgesic needs and response during labor, but require larger amounts of opioids post cesarean section: 70% more in women maintained on methadone and 50% more for women on Buprenorphine. Further, undertreating pain is associated with worse maternal outcomes upon discharge including: persistent chronic pain, greater opioid use, delayed functional recovery, and increased postpartum depression, which are all factors associated with higher rates of relapse which can lead to overdose and death.

Current guidelines in obstetrical anesthesia encourage non-opioid strategies and opioid-sparing treatment modalities to be used whenever possible in patients with a history of opioid use disorder, although the data for these strategies to treat postpartum pain comes from non-opioid using patients and we do not have data to help guide us in the opioid using population. Recommended additional multimodal non-opioid strategies are currently non evidence-based in the MAT patient population are based on data extrapolated from post-operative pain studies in non-pregnant patients undergoing non-obstetric surgeries, and pain studies on pregnant patients without MAT use undergoing cesarean section. From this data, possible options for opioid-sparing strategies include Gabapentin, Clonidine, Magnesium, TAP block, Ketamine, and Dexamethasone.

For our study, we are most interested in an option that would be able to be administered consistently (same time/same way), that our own labor nurses could give, and without requiring the patient to have had an epidural placement. Further, Gabapentin, clonidine and ketamine are associated with CNS effects like sedation or confusion that could make health care providers less likely to be comfortable giving these women additional necessary narcotics due to possible worsened sedation or respiratory depression. Lastly, we wanted to give a drug that both obstetricians and pediatricians were comfortable with from extensive use in our maternal population. Thus, single administration IV dexamethasone was chosen for this study.

Dexamethasone has been used as an adjunct for post-operative pain management in many types of surgeries. Although no large randomized trials exist, several small trials suggest an analgesic and opioid sparing effect of dexamethasone post-operatively for both pregnant and non-pregnant patients; however these studies excluded patients on MAT.

---

1. Haight, Sarah C., et al. "Opioid use disorder documented at delivery hospitalization—United States, 1999–2014." *Morbidity and Mortality Weekly Report* 67.31 (2018): 845.
2. Raymond, Britany L., Bradley T. Kook, and Michael G. Richardson. "The opioid epidemic and pregnancy: implications for anesthetic care." *Current Opinion in Anesthesiology* 31.3 (2018): 243-250.
3. American College of Obstetricians and Gynecologists' Committee on Obstetric Practice. Committee Opinion No. 711: Opioid use and opioid use disorder in pregnancy. *Obstet Gynecol* 2017; 130:e81–e94.
4. Metz, Torri D., et al. "Maternal deaths from suicide and overdose in Colorado, 2004–2012." *Obstetrics and gynecology* 128.6 (2016): 1233.

5. Smid, Marcela C., et al. "Pregnancy-Associated Death in Utah: Contribution of Drug-Induced Deaths." *Obstetrics & Gynecology* 133.6 (2019): 1131-1140.
6. Meyer, Marjorie, et al. "Intrapartum and postpartum analgesia for women maintained on buprenorphine during pregnancy." *European journal of pain* 14.9 (2010): 939-943.

The dose chosen for our study (0.1mg/kg) was based on multiple other clinical trials for which this study designed was based on, including either pregnant patients undergoing c-sections or non-pregnant patients undergoing non-obstetric surgeries who were given perioperative dexamethasone. The following doses were used (eight referenced studies):

- Doses given for C-section studies: 8mg, 10mg, 16mg
- Doses given for non-c section operative studies: 0.1mg/kg in 3 studies (one with max up to 8mg), 16mg, 8mg

Our study will use weight-based dosing. This will help to prevent subjects from getting doses that are higher than the above listed studies for their body mass.

Participants will be asked at the time of consent if they agree to being contacted at 6 months and 12 months postpartum via phone call. The purpose of this phone call will be to follow up on continuation of their medication assistance therapy and inquire about any non-prescribed opioid use or illicit drug use. The purpose of this will be to assess if the adjuvant pain therapy of dexamethasone resulted in less opioid use and subsequent less risk of relapse in the postpartum period. We know from work by the Connecticut Maternal Morality Review Committee that over 1/3 of maternal deaths in Connecticut are related to substance abuse with the vast majority of these occurring in the remote postpartum period. This will be a separate part of the consent form and participants will have the option to consent to the study alone but not the follow up portion.

1. Mohtadi, Ahmadreza, et al. "The effect of single-dose administration of dexamethasone on postoperative pain in patients undergoing laparoscopic cholecystectomy." *Anesthesiology and pain medicine* 4.3 (2014).
2. Kjetil, Hval, et al. "The prolonged postoperative analgesic effect when dexamethasone is added to a nonsteroidal antiinflammatory drug (rofecoxib) before breast surgery." *Anesthesia & Analgesia* 105.2 (2007): 481-486.
3. Szucs, Szilard, et al. "Postoperative analgesic effect, of preoperatively administered dexamethasone, after operative fixation of fractured neck of femur: randomised, double blinded controlled study." *BMC anesthesiology* 16.1 (2015): 79.
4. Samona, Jason, et al. "Effect of intraoperative dexamethasone on pain scores and narcotic consumption in patients undergoing total knee arthroplasty." *Orthopaedic surgery* 9.1 (2017): 110-114.

6. Subject Population: Provide a detailed description of the types of human subjects who will be recruited into this study.

Subjects will include pregnant patients with a history of opioid use disorder who are compliant in their use medication assisted treatment (methadone, buprenorphine, suboxone) who are scheduled for cesarean delivery or who require a cesarean delivery during labor for non-urgent reasons, including

but not limited to arrest of dilation, arrest of descent, failed trial of labor, non-reassuring fetal heart tracing. As soon as individuals are identified as being eligible (in the clinic, at their pre-operative visit or on admission to the labor floor) they will be provided information on the study. Individuals will not be approached for consent unless they are scheduled for a cesarean delivery or require a non-urgent cesarean delivery out of labor (see inclusion criteria below)

7. Subject classification: Check off all classifications of subjects that will be specifically recruited for enrollment in the research project. Will subjects who may require additional safeguards or other considerations be enrolled in the study? If so, identify the population of subjects requiring special safeguards and provide a justification for their involvement.

 Children	 Healthy	 Fetal material, placenta, or dead fetus
 Non-English Speaking	 Prisoners	 Economically disadvantaged persons
 Decisionally Impaired	 Employees	 Pregnant women and/or fetuses
 Yale Students	 Females of childbearing potential	

NOTE: Is this research proposal designed to enroll children who are wards of the state as potential subjects?

Yes  No

8. Inclusion/Exclusion Criteria: What are the criteria used to determine subject inclusion or exclusion?

Inclusion: 18 years or older, English-speaking, history of opioid use disorder with current use of MAT during pregnancy, scheduled for cesarean delivery for their current pregnancy for any indication [examples of **elective c-section** (decision made for c-section to be performed prior to onset of labor): fetal malpresentation, suspected macrosomia, prior c-section, abnormal placentation, patient preference], negative toxicology screen upon admission to the hospital for their cesarean section, no prior administration of betamethasone for fetal lung maturity within 24h of their scheduled cesarean delivery or women who require a c-section out of labor for non-urgent reasons and have received information about the study and the consent upon admission to the hospital and therefore have had adequate time to review the consent prior to the delivery ( (Arrest of dilation, Arrest of descent, Failed induction of labor, Patient choice to discontinue trial of labor, Fetal malpresentation with no to minimal dilation (<4cm dilation), planned cesarean delivery at a later date presenting in labor or with rupture of membranes)

- Exclusion: under 18 years old, non-English speaking, screen positive for illicit substance(s) on their admission toxicology screen, require general anesthesia for their cesarean section due to maternal/fetal indication for non-anticipated urgency (thus no longer 'elective') or failure of adequate intra-operative pain control with spinal anesthesia, medical history including known cardiovascular disease, heart failure, uncontrolled hypertension (SBP  $\geq$ 160mmHg and/or DBP  $\geq$ 110mmHg), uncontrolled gestational or pregestational diabetes, active GI bleed or untreated peptic ulcer, untreated infectious diseases including tuberculosis or systemic candida, patients requiring a c-section out of labor for urgent reasons who have not received information about the study and the consent form upon admission to the hospital (Non-reassuring fetal heart rate tracing (persistent category II heart rate tracing), Category III fetal heart rate tracing, Acute placental abruption, Cord prolapse, Fetal malpresentation at advanced (>4cm dilation)).

9. How will eligibility be determined, and by whom?

Eligibility will be determined by review of the patient electronic medical chart by their obstetrics provider, who will be consenting them for the study, to assess their eligibility given their medical history as well as later determine exclusion laboratory criteria (admission toxicology screen)

10. Risks: Describe the reasonably foreseeable risks, including risks to subject privacy, discomforts, or inconveniences associated with subjects participating in the research.

Risks with single administration dexamethasone are most relevant for special populations that have been excluded from this study, including:

Cardiovascular disease: Heart failure and/or hypertension; use has been associated with fluid retention, electrolyte disturbances, and hypertension. Use with caution following acute MI; corticosteroids have been associated with myocardial rupture.

Diabetes: may alter glucose production/regulation leading to hyperglycemia.

Gastrointestinal disease: (diverticulitis, recent intestinal anastomoses, active or latent peptic ulcer, ulcerative colitis, abscess or other pyogenic infection) due to perforation risk

In regard to subjects who plan to breastfeed following delivery:

- Although the risk to newborns is unknown for any corticosteroid, use of dexamethasone is encouraged by ACOG (the ObGyn national body), and considered safe in pregnancy, especially for short term use. It is routinely given to mothers for fetal benefits, mainly lung maturity for suspected pre-term deliveries/neonates (ACOG Committee Opinion 713: Antenatal Corticosteroids for Fetal Maturity)
- When administered to lactating women, small amounts of corticosteroids entered human milk. Although data on the use of dexamethasone during lactation are not available, the American Academy of Pediatrics classified the corticosteroids prednisone and prednisolone as compatible with breastfeeding(Katz FH and Duncan BR: Entry of prednisone into human milk. *N Engl J Med* 293:1154, 1975. McKenzie SA et al.: Secretion of prednisone into breast milk. *Arch Dis Child* 50:894-6, 1975. Ost L et al.: Prednisolone excretion in human milk. *J Pediatr* 106:1008-11, 1985. Committee on Drugs, American Academy of Pediatrics. The transfer of drugs and other chemicals into human breast milk. *Pediatrics* 108:776-89, 2001.).
- If you plan to breastfeed your baby, this drug does appear in small quantities in breast milk and thus there is theoretical risk of use of corticosteroids have the potential to cause adverse events in a breastfeeding infant (eg, growth suppression, interfere with endogenous corticosteroid production) with chronic use, although information related to prolonged use is not available. Single doses of dexamethasone are considered compatible with breastfeeding; (WHO 2002).
- No data are available on the transfer of dexamethasone into human milk. It is likely similar to that of prednisone which is extremely low. Doses of prednisone as high as 120 mg fail to produce clinically relevant milk levels (equivalent of 18mg Dexamethasone). This product is commonly used in pediatrics for treating immune syndromes such as arthritis and, particularly, acute onset asthma or other bronchoconstrictive diseases. It is not likely that the amount in milk would produce clinical effect unless used in high doses over prolonged periods(Hale, Thomas W., and Hilary E. Rowe. *Medications and Mothers' Milk* 2017. Springer Publishing Company, 2016.).

- The half-life is 1 to 5 hours, with no drug at high enough levels to remain detectable in breast milk after one day.
- Breastfeeding while on corticosteroids carries minimal risk of exposure to the infant, which may be further decreased by nursing immediately before or more than 4 hours after the dose (Makol, Ashima, Kerry Wright, and Shreyasee Amin. "Rheumatoid Arthritis and Pregnancy." *Drugs* 71.15 (2011): 1973-1987 Ost L, Wettrell G, Bjorkhem I, et al. Prednisolone excretion in human milk. *J Pediatr* 1985 Jun; 106(6): 1008-11.).

Additional risk and reactions listed below are almost exclusively associated with repeated and/or high dose use and some are based on reports for other agents in this same pharmacologic class and may not be specifically reported for dexamethasone. (Frequency not defined):

*Cardiovascular:* Bradycardia, cardiac arrhythmia, cardiac failure, cardiomegaly, circulatory shock, edema, embolism (fat), hypertension, hypertrophic cardiomyopathy (premature infants), myocardial rupture (post-MI), syncope, tachycardia, thromboembolism, thrombophlebitis, vasculitis

*Central nervous system:* Depression, emotional lability, euphoria, headache, increased intracranial pressure, insomnia, malaise, myasthenia, neuritis, neuropathy, paresthesia, personality changes, pseudotumor cerebri (usually following discontinuation), psychic disorder, seizure, vertigo

*Dermatologic:* Acne vulgaris, allergic dermatitis, alopecia, atrophic striae, diaphoresis, ecchymoses, erythema, facial erythema, fragile skin, hyperpigmentation, hypertrichosis, hypopigmentation, perianal skin irritation (itching, burning, tingling; following IV injection), petechiae, skin atrophy, skin rash, subcutaneous atrophy, suppression of skin test reaction, urticaria, xeroderma

*Endocrine & metabolic:* Adrenal suppression, carbohydrate intolerance, Cushing syndrome, decreased glucose tolerance, decreased serum potassium, diabetes mellitus, fluid retention, glycosuria, growth suppression (children), hirsutism, HPA-axis suppression, hyperglycemia, hypokalemic alkalosis, menstrual disease, moon face, negative nitrogen balance, protein catabolism, redistribution of body fat, sodium retention, weight gain

*Gastrointestinal:* Abdominal distention, gastrointestinal hemorrhage, gastrointestinal perforation, hiccups, increased appetite, nausea, pancreatitis, peptic ulcer, pruritus ani (following IV injection), ulcerative esophagitis

*Genitourinary:* Defective (increased or decreased) spermatogenesis

*Hematologic & oncologic:* Kaposi sarcoma, petechial, tumor lysis syndrome

*Hepatic:* Hepatomegaly, increased serum transaminases

*Hypersensitivity:* Anaphylactoid reaction, anaphylaxis, angioedema, hypersensitivity

*Infection:* Infection, sterile abscess

*Neuromuscular & skeletal:* Amyotrophy, aseptic necrosis of bones (femoral and humeral heads), bone fractures, Charcot-like arthropathy, myasthenia, myopathy (particularly in conjunction with neuromuscular disease or neuromuscular-blocking agents), osteoporosis, rupture of tendon, steroid myopathy, vertebral compression fracture

*Ophthalmic:* Exophthalmos, glaucoma, increased intraocular pressure, subcapsular posterior cataract

*Respiratory:* Pulmonary edema

11. Minimizing Risks: Describe the manner in which the above-mentioned risks will be minimized.

Populations at greatest risk with receipt of single dose IV dexamethasone will be excluded from the study.

12. Data and Safety Monitoring Plan: Include an appropriate Data and Safety Monitoring Plan (DSMP) based on the investigator's risk assessment stated below. (Note: the HIC will make the final determination of the risk to subjects.)

- a. What is the investigator's assessment of the overall risk level for subjects participating in this study? minimal risk in pregnant women and fetuses (when no drug is taken), greater than minimal risk in non-pregnant subjects when taking drug
- b. If children are involved, what is the investigator's assessment of the overall risk level for the children participating in this study? As only data collection from the medical record will be performed on the infants there is minimal risk to infants participating in the study

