3. The investigation does NOT involve a route of administration or dosage level or use in populations or other factor that significantly increases the risks (or decreases the acceptability of the risks) associated with the use of the drug product Single use (rather than chronic or high-dose use) administration of dexamethasone in our select patient population (excluding patients at higher risk of adverse effects of the medication) at the standard dosage level does not involve a dosage level, route, or population that significantly increases the risk associated with the use of this drug. Please see additional text on breastfeeding information for safety in infants.	
4. The investigation will be conducted in compliance with the requirements for institutional (HIC) review and with the requirements for informed consent of the FDA regulations (21 CFR Part 50 and 21 CFR Part 56).	
5. The investigation will be conducted in compliance with the requirements regarding promotion and charging for investigational drugs.	

**Exempt Category 2** (all items i, ii, and iii must be checked to grant a category 2 exemption)

i. The clinical investigation is for an *in vitro* diagnostic biological product that involves one or more of the following (check all that apply):

- Blood grouping serum
- Reagent red blood cells
- Anti-human globulin

ii. The diagnostic test is intended to be used in a diagnostic procedure that confirms the diagnosis made by another, medically established, diagnostic product or procedure; and

iii. The diagnostic test is shipped in compliance with 21 CFR §312.160.

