**Exempt Category 4**

A clinical investigation involving use of a placebo if the investigation does not otherwise require submission of an IND.

2. Background Information: Provide a description of previous human use, known risks, and data addressing dosage(s), interval(s), route(s) of administration, and any other factors that might influence risks. If this is the first time this drug is being administered to humans, include relevant data on animal models.

Dexamethasone is a well-known and widely used long acting corticosteroid that is a strong anti-inflammatory agent. It has been used as an adjunct for post-operative pain management as well as improvement in perioperative nausea and vomiting in many types of surgeries. It decreases inflammation by suppression of neutrophil migration, decreased production of inflammatory mediators, and reversal of increased capillary permeability; suppresses normal immune response. Dexamethasone's mechanism of antiemetic activity is unknown.

The majority of known risks with use of dexamethasone are associated with prolonged and/or high dose administration, especially in patients with specific medical co-morbidities, where as there are minimal risks with the single administration as we plan to utilize in our study in patients without the previously discussed co-morbidities. For example, an adverse reaction possible with our proposed dosing administration includes hyperglycemia, especially in those patients with uncontrolled diabetes. Please see previously discussed text on breastfeeding information for safety in infants.

3. Source: Identify the source of the drug or biologic to be used. The subjects would receive

a) Is the drug provided free of charge to subjects?  YES  NO

If yes, by whom? Funding obtained for this project will be used to cover the cost of the medication (vs. placebo) for the patient and will be obtained through a grant from Women's Health Research at Yale – Pilot Project Program.

4. Storage, Preparation and Use: Describe the method of storage, preparation, stability information, and for parenteral products, method of sterilization and method of testing sterility and pyrogenicity. This drug is consistently stored on the labor and delivery floor with appropriate storage, preparation, and stability techniques and information established by health care providers at the testing hospital facility, YNHH.

Check applicable Investigational Drug Service utilized:

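### The steroid washout names only betamethasone, so a woman who has just had dexamethasone can be randomised, and non-study dexamethasone is neither limited nor named for recording through 72 hours

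*Combined protocol and SAP*

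**What the plan says.** Section I item 8 (Inclusion/Exclusion Criteria) has one steroid condition: "no prior administration of betamethasone for fetal lung maturity within 24h of their scheduled cesarean delivery". It covers one agent, one indication and one type of delivery. The exclusion list in the same item names no corticosteroid. A second entry route follows, opening "or women who require a c-section out of labor for non-urgent reasons". Among its examples is "planned cesarean delivery at a later date presenting in labor or with rupture of membranes".

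Elsewhere the protocol describes non-study uses of dexamethasone. Section I item 10 (Risks) says of it: "It is routinely given to mothers for fetal benefits, mainly lung maturity for suspected pre-term deliveries/neonates". Section II B item 2 (Background Information) mentions its use for pain "as well as improvement in perioperative nausea and vomiting in many types of surgeries". Section I item 3 lists it among the opioid-sparing options, and Section II B item 4 says it is kept on the labor and delivery floor.

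The safety argument assumes one dose. Condition 3 of the IND exemption rests on "Single use (rather than chronic or high-dose use) administration of dexamethasone in our select patient population", and Section II B item 2 speaks of "minimal risks with the single administration as we plan to utilize in our study".

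Section I item 4 sets pain and opioid assessments out to 72 hours. Section I item 13 has no rule for non-study steroid. Section IV item 1 lists pain medications among the data collected but names neither steroids nor antiemetics.

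**The concern.** By writing a washout, the protocol accepts that a recent corticosteroid could affect the comparison. The washout then leaves out the study drug. A placebo woman given dexamethasone in the operating room is partly treated, and an active-arm woman given it receives a second dose.

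Two things are at stake. The first is contrast: if part of each arm already carries dexamethasone, the observed difference shrinks toward zero unless the second dose adds as much as the first. With 40 women there is little room for that. The second is the safety rationale: exposed active-arm women would get more than the single administration on which the exemption and the minimal-risk statement rely.

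Use after the infusion is a separate matter. It follows treatment, so randomisation does not guarantee balance. The documents give no basis for its direction or size, so it is not sized here.

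**Working it through.** **Reading check.** No section excludes prior dexamethasone for any reason or over any window. None restricts or standardises it during surgery, in recovery or on the ward. The single administration described in Section I item 4 is the study dose; it does not limit open-label use.

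**Inputs from the documents.** 40 women (Section III, Targeted Enrollment); two-sided 0.05 and Student's t-test (Section I item 13); 5 to 5.5 years of data collection, that is 60 to 66 months (Section I item 2). No effect size, SD, power or allocation ratio is given, so the target of 40 cannot be reproduced.

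**Assumptions.** 1:1 allocation (20 per arm). Standardised effect d = 0.909, the value that gives 80% power with 20 per arm by the noncentral t. A share p of both arms is exposed before the infusion. A second dose adds a fraction r of the first dose's effect. The SD is constant.

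**Formula.** In unexposed women the arms differ by d; in exposed women by r × d. The average difference is d × [(1 − p) + p × r] = d × [1 − p(1 − r)].

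**Worst case, r = 0:**
- p = 2%: 0.909 × 0.98 = 0.891, power 78%
- p = 5%: 0.909 × 0.95 = 0.864, power 76%
- p = 10%: 0.909 × 0.90 = 0.818, power 71%
- p = 20%: 0.909 × 0.80 = 0.727, power 61%

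**Half added, r = 0.5:** the multiplier is 1 − p/2. Power is 79%, 78%, 76% and 71% for the same four values of p.

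**Fully added, r = 1:** the multiplier is 1 and power stays at 80%.

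Mixing exposed and unexposed women also widens the spread within arms. Allowing for this gives 70% and 58% at r = 0, and 77% and 75% at r = 1, for p = 10% and 20%.

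**Cost of replacing excluded women.** Extra women to reach 40 = 40/(1 − p) − 40. For p = 2%, 5%, 10% and 20% this is 0.8, 2.1, 4.4 and 10.0. Extra time at constant accrual = (60 to 66 months) × p/(1 − p): about 1, 3, 7 and 15 to 17 months. If a request to avoid non-study dexamethasone removed three quarters of exposure (an assumption), the extra women would be 0.2, 0.5, 1.0 and 2.1, and the delay at most about 3 months.

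**The case against.** The strongest reply is that exposure is not shown. The statement about routine antenatal use sits in a breastfeeding-safety paragraph, and the antiemetic statement concerns surgery in general. Neither describes practice in these women at this hospital, and the criterion itself suggests that betamethasone is the expected lung-maturity agent. This stands: the rate is unknown, and at a few percent the loss of power is small. Testing dexamethasone on top of usual care is also a legitimate pilot design. Even then, the amount of usual-care dexamethasone should be known at analysis.

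Four stronger readings are tempting and are not supported:

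- **Bias.** A reader might infer that prior dexamethasone biases the comparison. Exposure before the infusion is balanced in expectation; the effect is dilution, and there may be none if doses add fully.
- **No condition at all on the out-of-labor route.** That is one reading of the punctuation. On the same reading the route would also escape the other inclusion conditions listed before it, so shared conditions are at least as natural. The point is ambiguity.
- **Breach of a dose ceiling.** 0.1 mg/kg plus a further 8 mg passes 16 mg above (16 − 8)/0.1 = 80 kg. But 16 mg is only the largest dose listed in Section I item 4. The protocol's comparison there is relative to body mass, and the weights in the cited studies are not given. The half-life of 1 to 5 hours in Section I item 10 also argues against simply adding doses given many hours apart.
- **A ban on every systemic corticosteroid.** This goes beyond the gap shown and could cost many months of accrual.

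Part of the exposure may already be retrievable. Dexamethasone given as an analgesic adjunct arguably counts as a pain medication under Section IV item 1. Antiemetic use does not.

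**Conclusion.** The concern holds as a fault in a stated criterion. Followed as written, the rule turns away a woman given betamethasone for lung maturity before a scheduled cesarean and admits one who has just had the study drug. It is also unclear whether the rule reaches the out-of-labor route, and no safeguard applies after the infusion.

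The size is unknown because no exposure rate is documented. The power losses, from 2 percentage points at 2% exposure to 19 at 20%, are worst-case illustrations resting on assumed allocation, effect size and exposure, with a second dose adding nothing. They shrink as the second dose adds more. The departure from the single-dose rationale applies to any exposed active-arm woman, but the documents do not show that it causes harm. The point is worth acting on because the gap is clear and the remedy is cheap.

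**What to change.** 1. Reword the criterion in Section I item 8 to: no betamethasone or dexamethasone within 24 h before the study infusion, for scheduled and out-of-labor cesareans. Check antenatal doses at the existing chart review (Section I item 9). Ask the anesthesia team about intraoperative doses before randomising. Eligibility already depends on intraoperative events, such as "failure of adequate intra-operative pain control with spinal anesthesia", so the question fits the same step. If the masked infusion must be prepared before surgery ends, ask about planned antiemetics instead. That cannot confirm what was given, so item 3 is still needed.
2. Ask the anesthesia and postpartum teams to avoid non-study dexamethasone in consented women through 72 h unless clinically needed, with the treating team deciding.
3. Abstract any non-study corticosteroid (drug, dose, time) from Epic, from 24 h before the infusion through 72 h after, and report it by arm. Keep women exposed after randomisation in their assigned arm.

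The cost is one reworded criterion, one request to two teams and one more item from a record already being reviewed. One question must be answered without delaying the dose on arrival in recovery. Some exposed women may need replacing. The avoidance request should keep that number small for intraoperative use, but it does not affect antenatal courses.
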